### **6.4.2. Disease Status Follow-Up**

Subjects who discontinue study treatment for a reason other than disease progression will move into the disease status follow-up period and should be assessed every 8 to 9 weeks by radiologic imaging (SCLC/solid tumors) or blood/bone marrow assessment (AML/MDS/MF) to monitor disease status. Every effort should be made to collect information regarding disease status until (whichever occurs first):

- The start of new antineoplastic therapy.
- Disease progression.
- Death.
- The end of the study.

## **6.5. End of Study**

The end of the study may be designated as the timepoint when all subjects have discontinued the study or the sponsor terminates the study.

## **7. CONDUCT OF STUDY ASSESSMENTS AND PROCEDURES**

### **7.1. Administration of Informed Consent Form**

Valid informed consent must be obtained from the study subject before conducting any study-specific procedures using an ICF approved by the local IRB/IEC that contains all elements required by ICH E6, and describes the nature, scope, and possible consequences of the study in a form understandable to the study subject. Local and institutional guidelines for ICF content and administration must be followed; the original signed ICF must be retained by the investigator, and a copy of the signed ICF must be provided to the study subject. The informed consent process for each subject must be documented in writing within the subject source documentation.

### **7.2. Interactive Response Technology Procedure**

The IRT will be contacted to obtain a subject ID number when a subject enters screening. Upon determining that the subject is eligible for study entry, the IRT will be contacted to enroll the subject. Additionally, the IRT will be contacted at each regular study visit to update the study drug supply and cohort management.

### **7.3. Demography and Medical History**

#### **7.3.1. Demographics and General Medical History**

Demographic data and general medical history will be collected at screening.

#### **7.3.2. Disease Characteristics and Treatment History**

A disease-targeted medical and medication history will be collected at screening.

### **7.4. Prior and Concomitant Medications and Procedures**

Prior and concomitant medications and procedures will be reviewed to determine subject eligibility. All concomitant medications and measures must be recorded in the eCRF, and any medication received or procedure performed within 30 days before enrollment and up to the end of study will be recorded in the eCRF. The medication record will be maintained after signing the ICF to document concomitant medications, including any changes to the dose or regimen. Concomitant medications include any prescription, over-the-counter, or natural/herbal preparations taken or administered during the study period. Concomitant treatments and/or procedures that are required to manage a subject's medical condition during the study will also be recorded in the eCRF.

### **7.5. Safety Assessments**

#### **7.5.1. Adverse Events**

Adverse events will be monitored from the time the subject signs the ICF. Subjects will be instructed to report all AEs during the study and will be assessed for the occurrence of AEs throughout the study. In order to avoid bias in eliciting AEs, subjects will be asked general,

nonleading questions such as "How are you feeling?" All AEs (serious and nonserious) must be recorded on the source documents and eCRFs regardless of the assumption of a causal relationship with the study drug. The definition, reporting, and recording requirements for AEs are described in Section 8.

### **7.5.2. Physical Examinations**

Clinically notable abnormalities that are considered clinically significant in the judgment of the investigator are to be reported as AEs.

Physical examinations must be performed by a medically qualified individual such as a licensed physician, physician's assistant, or a nurse practitioner, as local law permits.

Clinically notable abnormalities that are considered clinically significant in the judgment of the investigator are to be reported as AEs.

#### **7.5.2.1. Comprehensive Physical Examination**

The comprehensive physical examination performed at screening will include height and body weight, and assessment(s) of the following organ or body systems: skin; head, eyes, ears, nose, and throat; thyroid; lungs; cardiovascular system; abdomen (liver, spleen); extremities; and lymph nodes; as well as a brief neurological examination.

#### **7.5.2.2. Targeted Physical Examination**

The targeted physical examination performed at all other visits will be a symptom-directed evaluation. The targeted physical examination will include body weight and assessment(s) of the body systems or organs, as indicated by subject symptoms, AEs, or other findings.

### **7.5.3. Vital Signs**

Vital sign measurements include blood pressure, pulse, respiratory rate, and body temperature. Blood pressure and pulse will be taken with the subject in the recumbent, semirecumbent, or sitting position after 5 minutes of rest. Clinically notable abnormalities that are considered clinically significant in the judgment of the investigator are to be reported as AEs.

### **7.5.4. Electrocardiograms**

All 12-lead ECGs will be performed with the subject in a recumbent or semirecumbent position after 5 minutes of rest. A single ECG is performed at the screening, EOT, and safety follow-up visits. Triplicate ECGs are performed on Cycle 1 Day 1 and Cycle 1 Day 15 at predose and 1, 2, and 6 hours postdose. A triplicate ECG is performed on Cycle 1 Day 8 approximately 24 hours after the last dose on Day 7; if a subject is being seen on Day 7 or Day 9 (study drug administration days), triplicate ECG should be performed before study drug administration. Note that triplicate ECGs should be performed with a 2- to 5-minute break between evaluations. Note that the timed schedule may change per emerging PK data.

The 12-lead ECGs will be interpreted by the investigator at the site to be used for immediate subject management; all ECGs will be collected and reviewed by a central ECG vendor. The decision to include or exclude a subject or withdraw a subject from the study based on an ECG flagged as "Abnormal, Clinically Significant" is the responsibility of the investigator, in

consultation with the sponsor's medical monitor, as appropriate. Clinically notable abnormalities that are considered clinically significant in the judgment of the investigator are to be reported as AEs.

### **7.5.5. Laboratory Assessments**

Sites will use their local laboratories for eligibility and ongoing safety assessments. Chemistry, hematology, coagulation panel, serology, lipid panel, and urinalysis will all be analyzed.

For MF subjects only: after 24 weeks, D15 visits of each cycle can be omitted, with medical monitor approval.

#### **7.5.5.1. Pregnancy Testing**

A pregnancy test will be required for all women of childbearing potential during screening, on Day 1 (before the first dose of study drug) and at the end of treatment visit. Serum or urine pregnancy tests will be conducted as outlined in [Table 8](#), as medically indicated, or per country-specific requirement. Urine pregnancy tests will be done locally. If a urine pregnancy test is positive, the results should be confirmed with a serum pregnancy test.

If the serum pregnancy test is negative after a urine test was positive, the investigator will assess the potential benefit/risk to the subject and determine whether it is in the subject's best interest to resume study drug and continue participation in the study.

## **7.6. Efficacy Assessments**

Objective assessment of tumor status is required using appropriate disease-specific techniques, and the investigator's assessment will be used to determine responses and will be logged into the eCRF. For SCLC/solid tumors subjects, Response Evaluation Criteria in Solid Tumors (RECIST) v1.1 ([Eisenhauer et al 2009](#)) will be used, and the recommended method for measuring and following tumor burden will be CT scan or MRI, to include the thorax, abdomen, and pelvis; the neck can be included if needed. Alternative modalities may be substituted for a CT scan at the discretion of the investigator, provided that the same modality is used throughout the study and the methodology is consistent with RECIST v1.1.

For AML subjects, the International Working Group Response Criteria for Acute Myeloid Leukemia ([Cheson et al 2003](#), [Appendix D](#)) will be used as the recommended method for measuring and following disease status. For MDS subjects, International Working Group Response Criteria for MDS ([Cheson et al 2006](#), [Appendix F](#)) will be used as the recommended method for measuring and following disease status. For MF subjects, the proposed Response Criteria for MF ([Tefferi et al 2013](#), [Appendix G](#)) will be used as the recommended method for measuring and following disease status.

The schedule for disease assessments will be at screening (this will be considered the baseline assessment) for all subjects and then once every 8 weeks throughout the study for solid tumor and once every 4 weeks for AML/MDS. The schedule for MF disease assessments will be at screening (this will be considered the baseline assessment), once every 4 weeks until Week 24, and once every 12 weeks after Week 24. For subjects who discontinue treatment for reasons other than disease progression, every effort should be made to continue monitoring their disease

status until the start of new anticancer therapy, documented disease progression, death, or end of study, whichever occurs first.

Bone marrow examination (aspirate and biopsy) is required at screening for subjects with diseases that are typically monitored through bone marrow examination, including AML, MDS, and MF. Note: subjects with a history of allogenic hematopoietic stem cell transplantation should have bone marrow collected and analyzed locally for the purposes of determining disease status (where applicable); however their sample does not need to be processed for sequencing due to chimeric potential.

Data from the pathology report result from the bone marrow examination will be captured in the eCRF. All bone marrow examinations should include a unilateral aspiration and biopsy with FISH and cytogenetic testing, when feasible and indicated. Subjects may be enrolled based on a biopsy only when a "packed marrow" precludes aspiration at the decision of the medical monitor. Results of assessments performed under standard of care before the signing of informed consent may be used as the baseline disease assessment in lieu of a study-specific procedure if performed within 60 days of the first dose of study drug (Cycle 1 Day 1) and if adequate archive material is available and there has been no anticancer therapy in the interim.

For disease assessment timepoints in AML, MDS, and MF that do not correspond to a bone marrow examination, peripheral blood myeloid blast percentage will be evaluated by microscopic evaluation or other appropriate methodology and will be used as appropriate in conjunction with other parameters (eg, cytopenias) in determining disease status.

For AML and MDS subjects, a bone marrow disease assessment is strongly encouraged during Cycle 2, preferably at Cycle 2 Day 1 for subjects who have a significant circulating blast count reduction (as determined by the investigator), including subjects who are not completely cleared of circulating blasts; a bone marrow biopsy and/or aspirates for response is to be performed at Cycle 4 Day 1 or earlier as clinically indicated, followed by every other month as clinically indicated, or upon circulating blood cell recovery to assess antileukemic activity (cytogenetic testing is not required if CR is not presented). Bone marrow examination schedule can be modified with approval from the medical monitor.

For MF subjects, bone marrow biopsy must be completed at screening or baseline visit, unless biopsy and data from previous 2 months are available. Additional biopsies will be performed at Week 24, Week 48, and every 24 weeks. If a biopsy is not possible or contraindicated, or the tissue requirement cannot be satisfied, this requirement may be waived with approval from the medical monitor.

For MF subject disease assessment with spleen palpation: spleen length will be assessed by manual palpation at every study visit (laboratory-only visits not included) and will be used for routine subject management. Investigators should use a soft centimeter ruler so that palpable spleen length is measured in centimeters and not in finger breadths. The edge of the spleen shall be determined by palpation and measured in centimeters, using a soft ruler, from the costal margin to the point of greatest splenic protrusion. Spleen length must be recorded on the CRF.

## 7.8. Pharmacokinetic Assessments

### 7.8.1. Blood Sample Collection

Pharmacokinetic samples will be obtained at the visits indicated in the Schedule of Laboratory Assessments (Table 8) to evaluate plasma PK parameters as described in Appendix C. For PK sample collection, the following will be recorded:

- The exact date and time of the blood sample.
- The date and time of the last dose of study drug before blood collection (if applicable).
- The time of the most recent meal.

Subjects will receive reminder cards in advance of the study visit providing instructions to prepare for the visit (see Section 7.10.1). Instructions for plasma preparation and sample shipping will be provided in the Laboratory Manual.

#### 7.8.1.1. Timed Pharmacokinetic Testing

Timed PK testing will be performed using the timepoints shown in Table 10. The timing of PK sample collection may be coordinated with other timed tests (████████ ECG). On these study dates, the subject should arrive at the research unit in the morning. If study drug has been previously dispensed, the reminder card (see Section 7.10.1) will remind the subject to refrain from taking the study drug at home that day. Subjects will also be reminded about fasting requirements, as applicable (see Table 10). A trough (predose) PK sample will be collected early in the study visit, followed by administration of the study drug and subsequent timed blood samples. The study drug will be administered with approximately 240 mL of water. Subjects should remain fasting from food or water for at least 1 hour postdose, after which a meal or snack may be consumed.

Adjustments to the timing of postdose blood collection may be made based on emerging PK data, and additional sampling may be performed if emerging data suggest that drug exposure confirmation is required for subject safety; however, no more than 6 postdose timepoints will be used on a given day.

**Table 10: Pharmacokinetic Sample Schedule**

Visit	Predose	0.5 h ± 10 min	1 h ± 15 min	2 h ± 15 min	4 h ± 15 min	6 h ± 30 min
Cycle 1 Day 1 a	X	X	X	X	X	X
Cycle 1 Day 8	X					
Cycle 1 Day 15 a,b	X	X	X	X	X	X
Cycle 1 Day 22	X					
Cycle 2 Day 1 a,c	X	X	X	X	X	X

a No food intake 4 hours before dose and 1 hour after dose.

b In case of dose interruption, the new timing of PK sampling should be discussed with sponsor.

c Subjects in food-effect study only.

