#### **INCB059872/Study Drug, Dosage, and Mode of Administration:**

INCB059872 will be self-administered orally QOD or QD on a 28-day cycle. In each cycle of the QOD dosing schedule, subjects should receive 14 doses of INCB059872. In each cycle of the QD dosing schedule, subjects should receive 28 doses of INCB059872. Tablets will be available in 1 mg strength. The initial starting dose for Part 1 will be 2 mg QOD. The initial starting dose for other parts of the study will be based on the aggregate data review of Part 1.

For QOD administration, if a dose is missed by more than 24 hours, the subject should skip the dose and take the next scheduled dose at the usual time. For QD administration, if a dose is missed by more than 4 hours, the subject should skip the dose and take the next scheduled dose at the usual time. INCB059872 tablet should be taken on an empty stomach if possible (refrain from food consumption during the period 2 hours before and 1 hour after taking INCB059872). For subjects participating in the food-effect portion of the study in Part 2, TG B1, a high-fat, high-calorie meal will be consumed within 30 minutes before taking INCB059872 on Cycle 2 Day 1.

*Alternative dosing regimens (ie, once daily) may be explored based on emerging PK/■ and safety data.*

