**Table 8: Schedule of Laboratory Assessments**

Local Laboratory Tests	Protocol Section	Screening	Treatment						EOT	Safety Follow-Up	Notes			
			Cycle 1			Cycles 2+								
			Day 1	Day 8 (± 2 Days)	Day 15 (± 2 Days)	Day 22 (± 2 Days)	Day 1 (± 2 Day)	Day 15 (± 2 Days)						
Serum chemistries	Table 9	X	X*	X	X	X	X	X	X	X	* May be performed 3 days before the first dose.			
Hematology*	Table 9	X	X**	X	X	X	X	X	X***	X	* Must be drawn twice a week for the first 2 weeks of study treatment. In addition to Cycle 1 Day 1 and Cycle 1 Day 8, hematology samples should be drawn at Cycle 1 Day 4 ± 1 day and Cycle 1 Day 11 ± 1 day. ** May be performed 3 days before the first dose. *** Must be drawn twice a week for 2 weeks after last dose.			
Lipid panel	Table 9	X	X	X	X	X	X	X	X	X				
Coagulation panel	Table 9	X					X*		X		* Cycle 2 Day 1 and then every 3 cycles thereafter.			
Hepatitis screening	Table 9	X												
Urinalysis	Table 9	X					X*				* Cycle 2 Day 1 and then every 3 cycles thereafter			
Pregnancy test	Table 9	X*	X**						X**		All female subjects of childbearing potential. * Serum ** Urine			
PK plasma (predose)	7.8.1		X	X	X	X	X*				Collect before morning dose of study drug. * Cycle 2 Day 1, only for food-effect testing in Part 2.			
PK plasma TIMED (postdose)	7.8.1.1		X*		X*		X**				* Collect at 0.5, 1, 2, 4, and 6 hours after INCB059872 dose. Excess sample will be used for [redacted] analysis. ** Cycle 2 Day 1 only for food-effect study.			

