### 7.8.4. Food-Effect Pharmacokinetic Testing

Pharmacokinetic testing for food effect on drug exposure will be performed on approximately 8 subjects enrolled in TG B1, Part 2; this will occur on Cycle 2 Day 1.

Subjects will have been fasted from food (not including water) for at least 4 hours. A standardized high-fat, high-calorie breakfast will be given to these subjects approximately 30 minutes before administration of study drug. Subjects must consume the entire breakfast within 25 minutes, and INCB059872 administration will begin 5 minutes after completing breakfast.

A high-fat, high-calorie meal (approximately 800-1000 calories, approximately 50% calories from fat) ([FDA 2002](#)) may consist of the following:

- 2 eggs fried in butter
- 2 strips of bacon
- 1 English muffin with butter
- 4 oz hash brown potatoes
- 8 oz whole milk

Alternative menus with the same caloric and fat content may be substituted with the prior approval of the study sponsor.

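### The Cycle 2 Day 1 row of Protocol Table 10 bars food before the dose, yet it covers only food-effect subjects, who must eat a high-fat breakfast just before that dose

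*Protocol*

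**What the plan says.** Table 10 lists five PK visits. Three have full profiles (Cycle 1 Day 1, Cycle 1 Day 15 and Cycle 2 Day 1), and all three carry footnote a: "No food intake 4 hours before dose and 1 hour after dose". The Cycle 2 Day 1 row also carries footnote c: "Subjects in food-effect study only". Table 8 agrees, describing the predose sample at that visit as "Cycle 2 Day 1, only for food-effect testing in Part 2" and limiting the timed samples in the same way.

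The food-effect instructions appear in three places:

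- The synopsis (study drug, dosage and administration) and Section 5 give the same sentence for the TG B1 food-effect subjects: "a high-fat, high-calorie meal will be consumed within 30 minutes before taking INCB059872 on Cycle 2 Day 1".
- Section 7.8.4 sets the scale: "Pharmacokinetic testing for food effect on drug exposure will be performed on approximately 8 subjects enrolled in TG B1, Part 2". It places the test on Cycle 2 Day 1.
- Section 7.8.4 also sets the sequence. First comes a fast: "Subjects will have been fasted from food (not including water) for at least 4 hours". A standardized breakfast is then served about half an hour before dosing: "Subjects must consume the entire breakfast within 25 minutes, and INCB059872 administration will begin 5 minutes after completing breakfast".

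Section 7.8.1.1, which governs the timed PK visits, sends the reader to Table 10 for the fasting rule: "Subjects will also be reminded about fasting requirements, as applicable (see Table 10").

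**The concern.** The same row of the same table both identifies the food-effect subjects and tells them not to eat in the hours before the dose. Staff working from the PK schedule on the day would find a food ban where the procedure section tells them to serve a meal.

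At stake is the food-effect part of a secondary objective (Protocol Section 2.1.2, SAP Section 2.2.2). Cycle 2 Day 1 is the only PK visit with a planned meal. The other two full-profile visits are fasted under the same footnote, and Cycle 1 Days 8 and 22 have predose samples only. A Cycle 2 Day 1 profile taken without the meal cannot be replaced from another visit. If such a profile stayed in a comparison of fed and fasted exposure, it would pull the estimate toward no food effect. If it were removed, a sample of about 8 would be smaller.

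**Working it through.** The plan gives no figure to reproduce here. The check is whether any meal timing meets both instructions. Times are in minutes, with the dose at 0.

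**Inputs**

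- Food ban (Table 10, footnote a): 4 hours before to 1 hour after the dose, that is −4 × 60 = −240 to +60.
- Breakfast (Section 7.8.4): served at about −30, eaten within 25 minutes, dose 5 minutes after it is finished.
- Meal (synopsis and Section 5): within the 30 minutes before the dose, so between −30 and 0.

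**Step 1: who is bound by footnote a on this row.** Footnote c and Table 8 both limit Cycle 2 Day 1 sampling to the food-effect subjects. Footnote a on this row therefore cannot be meant for anyone else.

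**Step 2: overlap.**

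- Length of the ban: 240 + 60 = 300 minutes.
- Breakfast at its full length: −30 to −5, which is 25 minutes.
- Start of breakfast after the ban opens: 240 − 30 = 210 minutes.
- Overlap: 25 of 25 minutes.

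**Step 3: does any allowed timing escape?** Let the meal last m minutes, with m no more than 25. Since dosing follows 5 minutes after the last bite, the meal runs from −(m + 5) to −5. For every permitted m this lies between −30 and −5, inside −240 to +60. The meal in the synopsis and Section 5, between −30 and 0, lies inside as well. No permitted timing meets both rules.

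**Step 4: the alternative reading.** Suppose the 4 hours were meant to run back from the start of breakfast. The fast would then run from −30 − 240 = −270 to −30, and the breakfast would begin as it ended. On that reading the conflict disappears, and the fast of at least 4 hours in Section 7.8.4 is met. But footnote a counts from the dose and makes no exception for the breakfast.

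**Step 5: the postdose hour.** The ban from 0 to +60 does not touch the breakfast, and Section 7.8.1.1 separately asks for at least an hour of postdose fasting. Only the predose part of footnote a is in conflict.

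**The case against.** The strongest reply is that this is a footnote slip with an obvious intent. The meal is stated three times, and Section 7.8.4 is devoted to it, down to calories, fat content and a sample menu. Footnote c itself labels the row as the food-effect study, and so does the on-site dosing note in Table 7. A reader would normally let the specific section govern a generic footnote shared with two fasted visits. To dose a subject fasted, staff would have to ignore the one section that describes the test.

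The reminder route is also weaker than it first looks. The reference to Table 10 in Section 7.8.1.1 is qualified to apply only where relevant. A fasting reminder before arrival is consistent with the fast that Section 7.8.4 requires before breakfast. The visible reminder-card text in Section 7.10.1 covers withholding the morning dose and recording the last dose and last meal; it does not tell anyone to refuse a meal. A missed breakfast should also be detectable, because Section 7.8.1 records the time of the most recent meal and SAP Section 5.3.3 has the pharmacokineticist review records for exclusions.

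Most of this stands, and it is why the point is minor. It does not remove the contradiction. The synopsis and Section 5 follow their empty-stomach rule with an express instruction for food-effect subjects; Table 10 has no such carve-out. Detection afterwards also cannot recover a fed profile that was never collected.

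A reader might infer more than the documents support:

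- **That the food-effect comparison will be lost.** The intent is plain and the safeguards above exist, so this does not follow.
- **That each fasted subject's share of the sample measures the bias.** That share describes a hypothetical subject who is dosed fasted and kept despite review. Nothing in the documents says how many there would be.
- **That every site serving the breakfast will be recorded as deviating.** SAP Section 6.3 says only that deviations recorded on the eCRF are summarized and listed. Whether this would be recorded is not stated.
- **That the SAP has no planned fed-versus-fasted analysis.** That is a separate question, and blacked-out text in both documents may already answer it.

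**Conclusion.** The inconsistency is real as written. On the Cycle 2 Day 1 row, footnote a bars the meal that the synopsis, Section 5 and Section 7.8.4 require of the only subjects the row covers. The overlap is complete, and all of the approximately 8 planned food-effect subjects are subject to both instructions.

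The practical consequence is limited. Footnote a most likely carries over the fast that Section 7.8.4 places before breakfast, and widespread fasted dosing is unlikely. What remains is the risk that a site working literally from Table 10 takes the only planned fed profile in the fasted state. With so few subjects, each lost fed profile matters to the food-effect objective. No expected number of affected subjects and no expected bias can be derived.

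The conclusion rests on reading footnote a as written, with its hours counted from the dose, and on footnote c and Table 8 as the definition of who is sampled. It needs no outside figure. It is a minor correction to an operative sampling table and does not question the food-effect design.

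**What to change.** Reconcile the Cycle 2 Day 1 row of Table 10 with Section 7.8.4. One way is to replace marker a on that row with its own footnote, referring to Section 7.8.4 for the pre-meal fast and the breakfast and to Section 7.8.1.1 for the postdose fast. Footnote a can stay unchanged on the Cycle 1 Day 1 and Day 15 rows.

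The cost is one footnote, with no new visit, sample or data item. Section 10.1 requires sponsor and then IRB/IEC approval for changes to Protocol procedures, so the simplest route is to include the correction in the next protocol change.
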